**1.0 SUMMARY OF STUDY (Abstract with a maximum of 300 words)**

This study will address the efficacy of using low dose bupivacaine spinal anesthesia (SA) in combination with epidural volume extension (EVE) for pregnant patients undergoing short obstetric procedures. The use of neuraxial anesthesia – spinal, epidural, or combined spinal-epidural (CSE) – is standard of care in this patient population. However, one downfall of neuraxial anesthesia is the prolonged post-anesthesia care unit (PACU) stays patients incur while waiting for the numbness to subside after having a short procedure. The aim of this study is to determine if low doses spinal bupivacaine in conjunction with EVE can decrease the PACU recovery time for short obstetric procedures while still providing an adequate surgical block.

This study will be conducted at the UAB Women and Infants Center on the labor and delivery unit. Patients undergoing short (<1 hour) surgical procedures such as cerclage placement or dilation and curettage (D&C) for fetal demise will be recruited for this study. Inclusion criteria: patients undergoing short obstetric procedure in the operating room (OR) requiring spinal anesthesia. Exclusion criteria: BMI >35, coagulopathy, platelets <80,000, allergy to local anesthetic or fentanyl, previous spinal surgery, and spinal or intracranial mass.

Once informed consent is obtained, study participants will be randomized into two different groups: low dose spinal bupivacaine with EVE (BE), and standard-dose spinal bupivacaine (B). Spinal anesthesia will be administered via CSE in routine fashion by a qualified anesthesia provider that is independent of this study. The primary outcome will be total PACU time defined as the time from admission to PACU until the time patient meets PACU discharge criteria (Modified Bromage scale of < 2, blood pressure and heart rate within 20% of baseline, return of baseline oxygenation status as measured by pulse oximetry, alert with baseline mentation, pain well controlled) (Modified Bromage scale: 0-ability to maintain leg lift for prolonged period; 1- ability to lift legs briefly; 2- ability to bend knees; 3- ability to wiggle toes; 4- no movement of lower extremities). Secondary outcomes will be: (1) time until sensory level of T10 achieved, (2) degree of peak motor block after spinal placement (3) time until return of motor function (Modified Bromage score < 2), (4) duration of the block (defined as time from placement until PACU discharge criteria met), (5) quality of the block (as determined by any pain reported during surgery and/or the need to supplement through the epidural) and (6) patient satisfaction (based off of a 0-10 scale). A total of 40 patients will be recruited for the study.

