### 4.0 OBJECTIVE(S) & HYPOTHESIS

**Purpose:** The purpose of this study is to conduct a single site, prospective, randomized study to compare low-dose bupivacaine with fentanyl in combination with EVE to our traditional bupivacaine dose with fentanyl for short obstetric procedures.

**Outline of Therapy:** Patients who are undergoing either placement of cerclage or D&C will be randomized into two groups: 2 ml of preservative-free, isobaric bupivacaine 0.5% (10mg) with 12.5mcg of fentanyl (Group B), or 1 ml of preservative-free isobaric Bupivacaine 0.5% (5mg) with 12.5mcg of fentanyl (Group BE). Group B will serve as our control group. Each group will receive the spinal medications via a CSE technique. The epidural catheter will then be inserted into the epidural space in the B group, whereas a 10 mL bolus of sterile

saline will be injected through the epidural needle into the epidural space before the epidural catheter is threaded in the BE group. All CSEs will be placed by certified anesthesia providers working at UAB's WIC. Also, the epidural catheters that are placed in both groups can be used at any time throughout the procedure if the surgical anesthesia level is believed to be inadequate. Standard demographic data (age, height, and weight) will be collected in addition to data pertaining to primary and secondary endpoints.

**Primary endpoints or outcomes:** The primary outcome will be time until PACU discharge requirements are met (modified bromage scale of < 2, blood pressure and heart rate within 20% of baseline, return of baseline oxygenation status, alert with baseline mentation, pain well controlled).

**Secondary endpoints or outcomes:** Secondary outcomes will be the time elapsed to achieve T10 sensory level to pinprick, degree of peak motor blockade (recorded at the time of consecutive identical dermatomal sensory levels), time elapsed until motor block regresses to modified Bromage score < 2, duration of the block, quality of the block (as determined by any pain reported during surgery and/or the need to supplement through the epidural), and patient satisfaction.

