## 5.0 INTERPRETATION OF EXPECTED RESULTS

For each CSE performed, multiple factors will be recorded: patient's age, height, weight, time to onset of T10 sensory level, peak sensory level and peak level of motor block (described by modified Bromage scale), patient pain during surgery, need to use epidural catheter, time to return of motor function, and length of PACU stay. Data will be analyzed by our statistician looking for significant differences in outcomes in the BE group compared to the B group.

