## 8.0 STUDY INTERVENTIONS/PROCEDURES

### 1. **Study design.**

There will be two groups in this study differentiated by the dose of LA: 10 mg of preservative-free isobaric bupivacaine with 12.5mcg of fentanyl (B) and 5 mg of preservative-free isobaric bupivacaine with 12.5mcg of fentanyl (BE). Patients undergoing cerclage placement or D&C who meet the inclusion/exclusion criteria will be approached about the study. Informed consent will be obtained, and the patient will be randomized into either the B or BE group. The CSE will be performed by a certified anesthesia provider at UAB in the standard fashion. Patients in the B group will have an epidural catheter placed after the spinal. Patients in the BE group will receive a 10 mL bolus of sterile saline through the epidural needle before the epidural catheter is placed. Routine care will be provided to the patient throughout the procedure by an anesthesia provider that is independent of the study. This includes administering LA through the epidural catheter to ensure patient comfort during the surgery. Data pertinent to the study will be recorded on the IRB-approved data sheet that will be kept locked in a secure cabinet in the PI's office. Information recorded will include: time of spinal placement, presence of epidural saline bolus, drugs administered, time to achieve T10 sensory level to pinprick, peak sensory and motor block, PACU times, and patient satisfaction with her anesthetic. Information from the data sheet will be

transferred to a secured password protected database. Once a sufficient number of participants have been recruited, our data will be assessed by a statistician.

2. **Comparison groups.**

(B) Preservative-free isobaric bupivacaine 10 mg with 12.5mcg of fentanyl  
 (BE) Preservative-free isobaric bupivacaine 5 mg with 12.5mcg of fentanyl with addition of 10 mL of sterile saline for EVE

3. **Study and timeline of interventions.**

Discussion of the study to potential participants and obtaining informed consent will take about 15 minutes. As patients will receive routine care, no added time will be needed to perform this study. Therefore, routine CSE placement will take about 15 minutes, the operative procedure about 1 hour, and PACU recovery about 1 hour. Total time for recruitment and completion of the study will take approximately 2 hours and 30 minutes per patient, with 2 hours and 15 minutes being routine care. Total recruitment will take approximately one year to complete.

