4. **Measured end-points and timeline of end-point measurements.**

All endpoints will be measured prior to discharge from the WPACU

- a. Time until WPACU discharge criteria met
- b. Time elapsed until T10 sensory level achieved
- c. Time until score of <2 reached on Modified Bromage scale
- d. Duration of the spinal block
- e. Patient satisfaction of a scale of 1-10
- f. Patient pain during surgery
- g. Need to use epidural during surgery

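### The block-quality outcome does not count rescue outside the epidural, so a patient rescued that way with no reported pain and no epidural use is missed as a block failure

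*Combined protocol and SAP*

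**What the plan says.** Section 1.0 gives secondary outcome (5) as "quality of the block (as determined by any pain reported during surgery and/or the need to supplement through the epidural". Section 4.0 repeats it: "quality of the block (as determined by any pain reported during surgery and/or the need to supplement through the epidural), and patient satisfaction". The endpoint list in Section 8.0 (item 4) splits it into f, "Patient pain during surgery", and g, "Need to use epidural during surgery". Section 5.0 records the same two items: "patient pain during surgery, need to use epidural catheter, time to return of motor function, and length of PACU stay".

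Under study design, Section 8.0 leaves intraoperative care to a provider independent of the study, as routine care, and adds "This includes administering LA through the epidural catheter to ensure patient comfort during the surgery". The data sheet also takes "time of spinal placement, presence of epidural saline bolus, drugs administered, time to achieve T10 sensory level to pinprick", but no section links the drugs given to block quality or asks why a drug was given.

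The hypothesis in Section 4.0 is that the BE group meets discharge criteria sooner and also has adequate surgical anesthesia. Section 11.0 leaves block quality out of both its list of secondary endpoints and its secondary analysis. It does plan chi-square and Fisher's exact tests for categorical data in general.

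**The concern.** An outcome meant to show whether a block was good enough should register every way in which a block can be found wanting. This one registers two. The care described is wider than that: giving local anesthetic through the catheter is presented as part of routine care, not as the only permitted response. A provider who sees a low or patchy level may give an intravenous or inhaled drug, or convert to general anesthesia, before the patient complains and without dosing the catheter. Sedation or general anesthesia then also suppresses any later report of pain, which is the other signal.

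At stake is the second half of the hypothesis. Time to T10 describes onset, so block quality is the main planned evidence on adequacy during surgery. If inadequate blocks are more frequent with the lower spinal dose, uncounted rescues would make BE look closer to B than it is.

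**Working it through.** **1. Which patients does the definition capture?** Apply the two components to the possible courses of a patient whose block is inadequate.

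| Course | Pain reported | Epidural used | Captured? |
|---|---|---|---|
| Reports pain, then any rescue | yes | either | yes |
| No pain reported, epidural dosed | no | yes | yes |
| No pain reported, systemic or inhaled drug only | no | no | no |
| No pain reported, general anesthesia without epidural dosing | no | no | no |

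The gap is the last two rows.

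**2. Do the documents leave those rows open?** Section 4.0 says the catheters can be used if the level seems inadequate; it does not say they must be tried first. The Section 8.0 sentence on epidural local anesthetic gives an included example. Section 9.0 lists concomitant therapies as none, with no rule on supplemental drugs during surgery. The rows are therefore possible, but no section says how often to expect them.

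**3. Size per patient.** The plan states no figure for this outcome, so there is none to reproduce; the power figures in Section 11.0 concern PACU stay and are not used here. From Section 11.0, n = 20 per group. One missed patient changes the arm's rate by 1/20 = 5 percentage points, two by 10, three by 15.

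**4. Effect on a test (assumed counts).** Fisher's exact test, two-sided (Section 11.0 does not state sidedness), with no failures in B and k in BE, gives p = 2 × C(20,k)/C(40,k).

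- k = 5: 2 × 15,504/658,008 = 0.047
- k = 4: 2 × 4,845/91,390 = 0.106

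In this example one uncounted rescue moves the result across 0.05.

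**5. Range over the share missed (assumed rates).** Suppose true failure is 30% in BE and 5% in B, and the same share is missed in each arm. The counted rate is the true rate × (1 − share missed). Power is for Fisher's exact test at 0.05 with 20 per group.

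| Share missed | Counted BE | Counted B | Difference | Power |
|---|---|---|---|---|
| 0% | 30% | 5% | 25 points | 44.6% |
| 25% | 22.5% | 3.75% | 18.75 points | 27.8% |
| 50% | 15% | 2.5% | 12.5 points | 10.9% |

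Even when the same share is missed in both arms, the visible difference shrinks, because the arm with more failures loses more of them.

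**The case against.** A reader might infer that every patient rescued by intravenous or inhaled drugs or general anesthesia is scored as having an adequate block. The documents do not support that. Reported pain counts on its own, so a patient who complains and is then rescued by any route is captured. Nor do the documents contain an adequate/inadequate score; they say only what quality is determined by. A patient whose catheter fails is also a poor example: the outcome refers to the need to supplement, so she is arguably captured, and certainly if the catheter was dosed.

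A reader might also infer that missed patients cannot be found. The data sheet records the drugs given, and peak sensory level is recorded too, so some could be identified afterwards. What would be missing is the reason for the drug, and any classification made then would be post hoc.

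Two further objections carry weight. Both arms have a catheter available throughout, so rescue with neither pain nor epidural use may be uncommon. And the absence of block quality from Section 11.0 is arguably the larger omission. The first limits the likely size of the problem. The second is a reason to repair Section 11.0 at the same time. Neither closes the gap in the definition.

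**Conclusion.** The concern holds in a limited form. The definition omits non-epidural rescue and conversion to general anesthesia, so patients rescued in those ways with no reported pain and no epidural use are not captured as block failures. Each one moves her arm's rate by 5 percentage points. The number of such patients is unknown, and the counts and rates in the illustrations are assumptions.

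That the error favours BE is plausible but not shown. It rests on failures being more frequent at 5 mg than at 10 mg despite the saline extension, and on B not having a much larger share of its failures missed. This is a secondary outcome, so the primary comparison of PACU time does not depend on the definition, but the claim of adequate anesthesia does. Even with every failure counted, power at the assumed 30% v 5% is only 44.6%, so a non-significant test would not show that the arms are equally adequate.

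**What to change.** In Sections 1.0, 4.0 and 8.0 (item 4), extend the block-quality outcome to four components:

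- pain reported during surgery;
- epidural supplementation;
- any systemic or inhaled analgesic, sedative or anesthetic given because the block was inadequate;
- any conversion to general anesthesia.

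Score the two new components from the existing record of drugs given, with one tick box on the data sheet separating inadequate block from other reasons such as routine anxiolysis. Report each component and the composite by arm as counts. List the outcome in Section 11.0 among the secondary endpoints, with the Fisher's exact test already planned for categorical data.

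The cost is a short addition to the definition, one tick box and one entry in Section 11.0. Care does not change. Failure rates may look slightly higher in both arms, and attributing a sedative to an inadequate block involves some provider judgement; reporting the components separately lets readers see how much rests on it.

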**2. BACKGROUND & RATIONALE**

In OB anesthesia, a neuraxial technique is frequently used for a variety of surgical procedures as it is associated with reduced maternal morbidity and can provide for faster maternal bonding and a more direct experience during childbirth.

Multiple local anesthetics (LAs) can be used for this purpose, but each can come with undesired effects. Lidocaine was used frequently in the past for short surgical procedures due to its shorter duration of action; however, its use has declined significantly due to its high incidence of transient neurologic symptoms (TNS). Despite the high potential of cardiotoxicity when given in large doses, bupivacaine is widely used for SA because of its fast and reliable onset to surgical block. There have been many studies comparing the efficacy of different LAs for SA in lower extremity and abdominal surgeries with goals of T10 and T6 surgical levels respectively. The results prove the utility of bupivacaine in SA, but do note the presence of prolonged motor and sensory blockade at doses necessary for adequate analgesia compared to other LAs.

CSE is a popular and very common practice in anesthesia today as it offers reliable and quick anesthesia with the ability for the provider to administer subsequent medication to improve the efficacy of the block. It was originally thought that additional boluses of LA through the epidural increased the spread of the block through epidural analgesia as well as leakage of LA through the punctured dura into the intrathecal space. However, some studies have demonstrated a rise in analgesic level after administering only saline into the epidural space after first introducing intrathecal LA and/or opioids. One study looked at the difference of injecting equal amounts of LA or saline into the epidural space after induction of SA and found that both groups achieved similar levels, both of which were significantly higher than the group without EVE. Another small study looked at myelograms before and after injecting different amounts of saline into the epidural space. They found that contrast medium spread in a cephalad direction up to 4 levels and that the subarachnoid space decreased in diameter by over 25%. These studies suggest that increased volume alone in the epidural space can increase the surgical level of a SA.

Another advantage of the CSE technique is the ability to treat inadequate surgical anesthesia during surgery. If a spinal technique is performed, no additional medication can be given in the neuraxial space due to the fact it is just a one-time shot. With a CSE, an epidural catheter is placed in the epidural space after the spinal block is performed. This allows the provider to administer LA medication through the epidural catheter to maintain an adequate surgical block throughout the procedure. Therefore, if the spinal block begins to regress and the patient experiences any pain, LA can be administered through the epidural catheter to re-establish an adequate surgical block.

The ability to administer less bupivacaine will allow for a shorter duration of anesthesia and a quicker return to baseline function. Although we would like to reduce PACU times, we also understand the importance of providing an adequate surgical block. There is evidence that supports adequate surgical levels with low dose bupivacaine. One study has shown that equipotent doses of 10mg of bupivacaine with high opioid administration can produce up to T2 level

analgesia when combined with EVE. In this study, there was not only a significant difference in maximum block achieved, but also in time to onset of block. Yet another study demonstrated adequate analgesia for cesarean section when combining doses as low as 5mg of bupivacaine with EVE. Given that only a T10 level would be required for cerclage or D&C, it is reasonable to believe that low doses of bupivacaine combined with EVE would provide an adequate surgical block while reducing the time needed to recover from the spinal block.

### 3. SIGNIFICANCE OF STUDY

Neuraxial anesthesia remains the standard of care for parturients or recently postpartum patients requiring anesthesia for surgical procedures. At UAB, we routinely use 10-12mg of hyperbaric bupivacaine with 12.5mcg of fentanyl in our spinal anesthetics for these procedures. This combination effectively delivers fast and reliable analgesia for our patients, but also comes with the burden of prolonged sensory/motor blockade and ultimately an extended stay in PACU(>1 hour). Many of these patients are otherwise stable but must be maintained under our care until their motor block recedes. More time spent in the PACU equates to an increase in healthcare resource and cost consumption, much of which we do not recuperate. If we are able to demonstrate satisfactory surgical anesthesia with an agent that could provide a faster recovery and shorter PACU stay, we could decrease our cost of care for these cases. Another important factor that must be considered is patient satisfaction. It is thought that patients just recently having a D&C for fetal demise suffer emotional distress as they sit in PACU and hear all of the new mothers interact with their children for the first time. Decreasing the length of time in the PACU will decrease healthcare resource and cost consumption and potentially lessen some of the emotional hardships suffered by our patients.

### 4.0 OBJECTIVE(S) & HYPOTHESIS

**Purpose:** The purpose of this study is to conduct a single site, prospective, randomized study to compare low-dose bupivacaine with fentanyl in combination with EVE to our traditional bupivacaine dose with fentanyl for short obstetric procedures.

**Outline of Therapy:** Patients who are undergoing either placement of cerclage or D&C will be randomized into two groups: 2 ml of preservative-free, isobaric bupivacaine 0.5% (10mg) with 12.5mcg of fentanyl (Group B), or 1 ml of preservative-free isobaric Bupivacaine 0.5% (5mg) with 12.5mcg of fentanyl (Group BE). Group B will serve as our control group. Each group will receive the spinal medications via a CSE technique. The epidural catheter will then be inserted into the epidural space in the B group, whereas a 10 mL bolus of sterile

saline will be injected through the epidural needle into the epidural space before the epidural catheter is threaded in the BE group. All CSEs will be placed by certified anesthesia providers working at UAB's WIC. Also, the epidural catheters that are placed in both groups can be used at any time throughout the procedure if the surgical anesthesia level is believed to be inadequate. Standard demographic data (age, height, and weight) will be collected in addition to data pertaining to primary and secondary endpoints.

**Primary endpoints or outcomes:** The primary outcome will be time until PACU discharge requirements are met (modified bromage scale of < 2, blood pressure and heart rate within 20% of baseline, return of baseline oxygenation status, alert with baseline mentation, pain well controlled).

**Secondary endpoints or outcomes:** Secondary outcomes will be the time elapsed to achieve T10 sensory level to pinprick, degree of peak motor blockade (recorded at the time of consecutive identical dermatomal sensory levels), time elapsed until motor block regresses to modified Bromage score < 2, duration of the block, quality of the block (as determined by any pain reported during surgery and/or the need to supplement through the epidural), and patient satisfaction.

**Study Hypothesis:** We hypothesize that patients in the EVE group will meet the criteria for PACU discharge significantly quicker than the traditional bupivacaine group while having adequate surgical anesthesia. We also hypothesize that patients in group BE will reach a T10 sensory level quicker, have a lesser degree of peak motor blockade, and will have a faster recovery of motor function.

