#### **11.0 STATISTICAL CONSIDERATIONS**

**Demographic Variables:** Age, weight, height, past medical history, procedure type.

**Control Variables:** Group B (10 mg of preservative-free isobaric bupivacaine and 12.5 mcg of fentanyl) vs Group BE (5 mg of preservative-free isobaric bupivacaine and 12.5 mcg of fentanyl with 10 ml of sterile saline through epidural)

**Study Variables:** The primary endpoint is the time until PACU discharge requirements are met. The secondary endpoints are time elapsed to achieve T10 sensory level, degree of peak motor blockade, time elapsed until motor block regresses to modified Bromage score < 2, duration of the spinal block, and patient satisfaction score.

**General Data Analysis:** All demographic and clinical variables with continuous measures will be expressed as means and standard deviations; categorical factors will be expressed as proportions. For non-normal data, the medians and interquartile ranges will be displayed. The distribution of the continuous factors will be examined using the Kolmogorov-Smirnov test. For data that are normally distributed, One-way analysis of variance (ANOVA) will be used to compare the two types of anesthesia. For data that are not normally distributed, the Kruskal-Wallis test will be used for comparisons. Chi-square and Fisher's exact tests will be used to analyze categorical data. For all comparisons, a p-value less than 0.05 will be considered statistically significant.

**Primary Outcome Analysis.** The primary endpoint for this study is the length of time until PACU discharge requirements are met. One-way ANOVA (or the Kruskal-Wallis test, as appropriate) will be used to assess whether PACU length of stay is significantly associated with type of spinal anesthesia. Linear regression will also be used to evaluate the relationship between method of spinal anesthesia and PACU length of stay, while controlling for relevant clinical and demographic variables.

**Secondary Outcome Analysis:** One-way ANOVA will also be used to compare groups on time to achieve T10 sensory level, degree of peak motor blockade, time elapsed until motor block regresses, and patient satisfaction.

**Additional Data Analysis:** N/A

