**Statistical Power and Sample Size Estimates:** Approximately 40 subjects (20 per group) are expected to be enrolled in this study. Assuming a standard deviation of 20 minutes for PACU length of stay, a study with this sample size will have approximately 80.7% power to detect a 20 minute difference and approximately 98.9% power to detect a 30 minute difference in PACU length of stay between Group B and Group BE.

**Study Population Availability:** Approximately 3-5 of these procedures are performed per week, which equals about 200 cases per year. About 80% of these cases will be done under spinal anesthesia for a total of 160 per year. Assuming a 50% enrollment rate, it should take 7 to 8 months to complete enrollment.

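### With 20 per arm, a non-significant difference cannot support the adequate-anesthesia half of the hypothesis, and the plan sets no interval or benchmark for it

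*Combined protocol and SAP*

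**What the plan says.** Section 4.0 (Study Hypothesis) makes a two-part claim: BE patients will meet the PACU discharge criteria "significantly quicker than the traditional bupivacaine group while having adequate surgical anesthesia". Section 1.0 pairs the same two aims, and Section 3 rests the cost argument on showing that anesthesia was satisfactory.

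Section 4.0 supplies a measure of adequacy among the secondary outcomes: "quality of the block (as determined by any pain reported during surgery and/or the need to supplement through the epidural". Section 8.0 lists pain and epidural use as separate end-points.

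On inference, Section 5.0 says: "Data will be analyzed by our statistician looking for significant differences in outcomes in the BE group compared to the B group". Section 11.0 (General Data Analysis) says "Chi-square and Fisher's exact tests will be used to analyze categorical data" and "For all comparisons, a p-value less than 0.05 will be considered statistically significant". It also says that categorical factors will be shown as proportions. Neither the list of secondary endpoints in Section 11.0 nor its secondary analysis paragraph names block quality, so only the general rule for categorical data covers it.

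On size, Section 11.0 says "Approximately 40 subjects (20 per group) are expected to be enrolled in this study". Power is stated for PACU time only ("Assuming a standard deviation of 20 minutes for PACU length of stay"). No section gives an acceptable block-failure rate, a margin, a confidence interval or a power figure for block quality.

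**The concern.** Faster discharge is a superiority claim, and a difference test suits it. Adequate anesthesia is a claim that failures are acceptably few, and a difference test cannot establish that. If the test is non-significant, the data may fit both equal failure rates and a large excess of failures under half the intrathecal dose. With 20 patients per arm, that ambiguity is the likely outcome.

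The risk is a report that the low-dose technique shortened recovery with adequate anesthesia, when the trial had limited ability to reveal a substantial excess of intraoperative pain or top-ups. Adding block quality to the Section 11.0 list under the existing p<0.05 rule would not remove this problem.

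**Working it through.** **Inputs.** From Section 11.0: 20 per group; chi-square and Fisher's exact tests; significance at 0.05 (taken as two-sided, since sidedness is not stated). From Section 4.0: failure means any pain during surgery and/or epidural supplementation. Assumed, because the documents give no figure: a true BE failure rate of 20% and a control failure rate of 0% to 10%.

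**The plan's own power figure.** It concerns PACU time, not block quality. With SD 20 minutes and 20 per arm, a two-sided t-test (equivalent to two-group ANOVA) has power 86.9% for 20 minutes and 99.6% for 30 minutes. The stated 80.7% and 98.9% match 17 per arm, but the plan states no such loss. The stated figures are conservative. The mismatch is a separate matter and does not affect this point.

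**Smallest significant split when B has no failures.**
- 0/20 vs 4/20, Fisher: p = 2 × C(20,4)/C(40,4) = 2 × 4,845/91,390 = 0.106.
- 0/20 vs 5/20, Fisher: p = 2 × C(20,5)/C(40,5) = 2 × 15,504/658,008 = 0.047.
- 0/20 vs 4/20, uncorrected chi-square: 40 × (20 × 4)²/(20 × 20 × 4 × 36) = 4.44, p = 0.035.

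So with no control failures, Fisher needs five BE failures and uncorrected chi-square needs four.

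**Probability of missing a true 20% BE failure rate.** This is the sum of Bin(x; 20, control rate) × Bin(y; 20, 0.20) over all pairs (x, y) with p ≥ 0.05. With a control rate of 0% it reduces to P(Y ≤ 4) = 0.630 for Fisher and P(Y ≤ 3) = 0.411 for uncorrected chi-square.

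| Assumed control failure | Fisher | Uncorrected chi-square | Yates chi-square |
|---|---|---|---|
| 0% | 63.0% | 41.1% | 80.4% |
| 1% | 68.3% | 48.6% | 82.5% |
| 2% | 72.9% | 55.2% | 84.5% |
| 5% | 83.2% | 70.8% | 89.5% |
| 10% | 92.8% | 86.2% | 94.9% |

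If only 17 per arm were evaluable, the Fisher range would be 75.8% to 94.6%.

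**What intervals would show.**
- BE 0/20: exact (Clopper-Pearson) 95% upper limit = 1 − 0.025^(1/20) = 16.8%.
- BE 1/20 and 2/20: upper limits 24.9% and 31.7%.
- BE 4/20: 5.7% to 43.7%.
- Difference, 0/20 vs 0/20 (Newcombe): the Wilson upper limit is 1.96²/(20 + 1.96²) = 0.161 in each arm, so the interval is −16.1 to +16.1 points.
- Difference, BE 4/20 vs B 1/20 (Newcombe): −7.1 to +37.0 points. The Fisher p-value for the same data is 0.34.

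**The case against.** Four objections have substance.

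**The error is not written into the plan.** A reader might infer that the investigators will declare the block adequate whenever p ≥ 0.05. No section says so. Section 5.0 says what will be looked for, not what a null result means. Failure proportions will also be described, so a p-value is not the only thing on which adequacy could be judged. Both points stand. What remains is that no benchmark or interval accompanies the proportions, so no result is identified that would count against adequacy.

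**The numbers depend on the test and on assumed rates.** A reader might infer that a 1-in-5 failure rate would usually go undetected whatever the test. Section 11.0 names chi-square and Fisher without a rule for choosing. With uncorrected chi-square, 0/20 vs 4/20 is significant, and the miss rate is below one half when control failure is below about 1.2%. Fisher is the conventional choice here, since the assumed rates imply only 2 to 3 expected failures per arm (4 to 6 in total), but the plan does not commit to it.

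**Block quality is secondary, and failure is broadly defined.** The trial is sized on PACU time, and low power for a secondary binary outcome is ordinary in 40 patients. Both arms have a catheter for supplementation, so a failure here includes any reported pain or any top-up, not only a block that could not be used. This limits the weight of the point. It does not make a null test informative about a clause of the hypothesis.

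**A pass/fail limit would be nearly unattainable.** A limit of 16.8% or less on the BE failure rate cannot be met even with 0/20. At a true 5% rate, 0/20 occurs in only 0.95^20 = 36% of trials. This is correct, and it is why the remedy rests on estimation rather than on a compulsory limit.

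**Conclusion.** The point holds in a limited form. The plan's only inferential rule for block quality is a difference test at p<0.05, and a non-significant result from 20 per arm cannot support the claim of adequate anesthesia. Under an assumed control failure rate of 0% to 10%, a true 20% BE failure rate is missed in 63% to 93% of trials with Fisher and in 41% to 86% with uncorrected chi-square. The upper limit of 16.8% for 0/20 rests on no assumed failure rate.

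The documents do not support saying that the plan equates non-significance with adequacy, or that the trial has almost no ability to detect excess failures: power for 0% vs 20% is 37% with Fisher and 59% with uncorrected chi-square. Nor do they settle whether the adequacy clause is a comparison with B or a statement about BE alone; the argument applies to both. The primary PACU analysis is unaffected.

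**What to change.** In Section 11.0:
- Name block failure (pain during surgery and/or epidural supplementation) as an analysed outcome.
- Report the BE failure proportion with an exact (Clopper-Pearson) 95% confidence interval, and the BE minus B difference with a Newcombe or Miettinen-Nurminen 95% confidence interval.

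In Sections 5.0 and 11.0, state that a non-significant p-value will not be read as evidence of adequacy, and that the conclusion on adequacy is limited to the failure rates and differences that the intervals exclude.

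If the investigators also choose to fix a maximum acceptable failure rate before enrollment, the plan should say which of the two intervals it applies to. It should also acknowledge that 20 per arm cannot establish a BE failure limit of 16.8% or less. The choice of any such limit is theirs.

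Cost: a few lines of text and no added patients. The downside is that the adequacy conclusion will be weaker than hoped, and the firm conclusion may have to be confined to PACU time.
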